2.2 Secondary Objectives

2.2.1 To prospectively characterize MCD presentation in Malawi.

2.2.2 To determine overall survival rate.

2.2.3 To determine event-free survival rate.

2.2.4 To describe the efficacy of the risk-adjusted treatment protocol as determined by clinical response rates at end of treatment and 12 weeks after start of treatment.

2.2.5 To describe radiologic response rates at end of treatment and 12 weeks after start of treatment.

2.2.6 To further characterize the safety by describing the frequency of all AEs with risk-adjusted treatment-protocol for MCD in Malawi.

2.2.7 To describe the rate of Kaposi sarcoma exacerbation, as defined by symptomatic or clinical (dermatologic or visceral organ) exacerbation of disease in patients receiving the risk-adjusted treatment protocol.

2.2.8 To describe the quality of life of patients with MCD before, during and after treatment with a rituximab-based, risk-adjusted treatment protocol, as assessed by the MCD symptom score and PROs.⁴²

2.2.9 To describe the trends in hemoglobin, platelet count, C-reactive protein (CRP), and IL-6 before, during, and after a risk-adjusted, rituximab-based treatment protocol

for MCD in Malawi and describe the utility of these markers as a predictor of relapse.

2.2.10 To evaluate for predictors of relapse or refractory disease with a risk-adjusted, rituximab-based treatment protocol.

2.2.11 To evaluate changes in Kaposi sarcoma viral load as a result of treatment.

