3.2 Secondary Endpoints

3.2.1 At study entry, basic demographics and baseline laboratory values will be summarized using descriptive statistics (i.e., means, medians, and variability measures for continuous variable; rates and proportions for binary variables). Screening assessments to be completed within 21 days prior to study enrollment.

3.2.2 Overall survival will be assessed at 12 weeks, one year, and two years from the start of treatment.

3.2.3 Event-free survival will be defined as the rate of refractory disease, relapse (same definition of active disease as in the inclusion criteria in section 4.1), non-Hodgkin lymphoma development or death and will be assessed at 12 weeks, one year, and two years from the start of treatment.

3.2.4 Clinical response rate at end of treatment and 12 weeks from treatment initiation (clinical response defined as resolution of presenting signs/symptoms that defined

the Multicentric Castleman disease (MCD) attack) without relapse at 12 weeks. MCD attack/flare is defined in Section 4.1.1.

3.2.5 Radiologic response rate is the percentage of patients without relapse at end of treatment and 12 weeks from treatment initiation. Chest radiography and abdominal sonography will be used for staging. Per Revised response criteria for gross lymphadenopathy, response will be evaluated via complete survey of lymph nodes with measurements and physical assessment of other palpable masses with measurements.

Response criteria for lymph node response will be as follows: Complete response (CR)- disappearance of all evident disease; Partial response (PR)-at least 50% decrease in target lesions with no increase in non-target lesions, Stable disease (SD)- Neither sufficient shrinkage to qualify for PR nor sufficient increase to qualify for progressive disease (PD); PD- appearance of a new lesion or at least a 50% increase in lesion size.

3.2.6 Additional safety assessment will be graded by CTCAE v 5.0 through 12 weeks from the start of therapy.

3.2.7 Kaposi sarcoma exacerbation will be defined as new symptoms attributed to KS or clinically evident exacerbation of dermatologic or visceral disease. All disease flares will be biopsy confirmed whenever possible.

3.2.8 Quality of life will be assessed by the MCD symptom score, a patient-reported outcomes questionnaire, and PROMIS Global 10, at baseline (week 1), 15 days (week 3), end of treatment (week 5), 12 weeks, 6 months, and 24 months after treatment, and at the time of any relapse.

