7.1.7 Radiologic Disease Assessment (Revised response criteria for gross lymphadenopathy)

All patients will undergo baseline on-study chest radiography and abdominal sonography for staging. Response will be evaluated via complete survey of lymph nodes with measurements and physical assessment of other palpable masses with measurements (using a flexible metric ruler in two dimensions). Chest radiography and abdominal sonography will be repeated at completion of treatment.

Measurable disease will be defined as the presence of at least one measurable pathologic lymph node or other mass that can be accurately measured by physical exam in at least one dimension with the longest diameter a minimum size of 10mm caliper measurement by clinical exam (lesions which cannot be accurately measured with calipers should be recorded as non-measurable). All measurements should be recorded in metric notation using calipers. All baseline evaluations should be performed as close as possible to the treatment start and never more than four weeks before the beginning of treatment. The same method of assessment and the same technique should be used to characterize each identified and reported lesion at baseline and during follow-up. Clinical lesions will only be considered measurable when they are superficial and ≥ 10 mm diameter as assessed using calipers.

All measurable lesions by physical exam or maximum of five lesions should be identified as target lesions and will be recorded and measured in two dimensions at baseline. Target lesions should be selected on the basis of their size (lesions with the longest diameters) and should also be those that lend themselves to reproducible

repeated measurements. A sum of the product of diameters (SPD, as in the International Harmonization Product criteria) for all target lesions will be calculated and reported as the baseline SPD. The baseline SPD will be used as reference to further characterize the objective tumor response of the measurable dimension of the disease.

All other lesions (or sites of disease), including lesions evident only by chest x-ray or ultrasound given difficulties with reproducibility of radiographic studies in our setting, should be identified as non-target lesions and should also be recorded at baseline. Measurements are not required, and these lesions should be followed as 'present' or 'absent', or in rare cases 'unequivocal progression.'

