A similar strategy for response assessment based on target lesions documented by physical exam alone is currently being utilized at UNC Project Malawi for a clinical trial for lymphoma.

Response criteria for lymph node response will be as follows.

- Complete response (CR): Disappearance of all evident disease. Any pathological lymph node (LN), whether target or non-target, must have decreased to <10mm in diameter. Any non-target lesion evident by chest x-ray or ultrasound must also be documented to have resolved by repeat evaluation.
- Partial response (PR): At least a 50% decrease in SPD of up to six target lesions without any increase in size of non-target lesions.
- Stable disease (SD): Neither sufficient shrinkage to qualify for PR nor sufficient increase to qualify for PD.
- Progressive disease (PD): Appearance of a new lesion(s) >15mm in diameter, at least a 50% increase in SPD of more than one node, OR at least a 50% increase in diameter of a previously identified node >1cm. Given numerous causes of adenopathy in Malawi (particularly among HIV-infected individuals) and in order to exclude alternative non-lymphoma diagnoses, a concerted attempt to re-biopsy at the time of relapse or progression will be made unless patients refuse or the site is not amenable using locally available resources.

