8.0 EVALUATIONS AND ASSESSMENTS

8.1 Time and Events Table (Table 7)

Table 7: Time and Events Table.	Initial Visit or Relapse ¹	Treatment days 1, 8, 15, and 22 ²	End-of-treatment (Week 5)	Follow-up (12 weeks)	Long term follow up ⁴
Informed consent	Initial visit only				
History & physical exam ⁵	X	X	X	X	X
Concomitant medications ⁶	X	X	X		
ECOG performance status ⁷	X	X	X		
Toxicity evaluation ⁸	X	X	X	X	X ⁸
Tumor biopsy ⁹	X				
Survival ¹⁰		X	X	X	X
Treatments ¹¹		X			
Lymph node measurements	X	Day 15 only	X	X	X
MCD-SS and Quality of life assessment ¹²	X	Day 15 only	X	X	X ¹²
Chest X-ray and abdominal ultrasound	X		X ¹³		
Hematology & blood chemistries ¹⁴	X ¹⁵	X ¹⁶	X	CBC only	CBC only
Correlative blood samples ¹⁷	X	Day 15 only	X	X	X ¹⁹
Lactate dehydrogenase	X	Day 15 only	X		

Viral and host genotyping	X	
Urine pregnancy test	X ¹⁸	
Hepatitis B (for HIV-negative patients)	X	
CD4 and HIV RNA (if HIV positive)	X	X ¹⁹

¹ Screening assessments must be completed within 21 days prior to study enrollment.

² A window of +/- 7 days will apply to all study visits; however, lymph node measurements must take place prior to that cycle's treatment.

³ End-of-treatment visit should occur 7-14 days from final dose of chemotherapy. A subject who is being withdrawn for disease progression or for other reasons (e.g. unacceptable toxicity, etc.) should complete an end of treatment visit.

⁴ Long term follow-up will occur every 3 months until 24 months after the start of treatment unless otherwise noted.

⁵ After the initial visit (comprehensive history and physical exam) subsequent visits will address a focused history and physical exam.

⁶ All concomitant medications will be recorded.

⁷ See Appendix E. ECOG Performance Status

⁸ per NCI CTCAEv5.0 for notation of baseline toxicity. Assess from initial visit through first follow-up visit (12 weeks) and again at the final follow up visit (24 months).

⁹ Archival and/or fresh sample.

¹⁰ Survival will be assessed at each visit through out the duration of treatment, follow up, and long term follow up.

¹¹ Subjects with low risk disease will receive rituximab at 375 mg/m² weekly for 4 weeks. High risk subjects will receive rituximab at 375 mg/m² and etoposide at 100 mg/m² weekly for 4 weeks.

¹² Quality of life assessment includes PROMIS Global 10, MCD-SS and QoL will be assessed through follow up, and at 24 months during long term follow up. QoL will also be assessed at the time of any relapse.

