¹³ Omitted if no baseline abnormalities on chest x-ray and abdominal ultrasound.

¹⁴ Hematology assessments include hemoglobin, white blood cell count, white blood cell differential, and platelet count. Blood chemistry assessments include serum creatinine, total bilirubin, albumin, and the following as deemed necessary per SOC: sodium, potassium, chloride, bicarbonate, glucose, blood urea nitrogen, aspartate aminotransferase, alanine aminotransferase, and alkaline phosphatase. See the T&E table for when lactate dehydrogenase is measured.

¹⁵ If a patient has been tested for hemoglobin within 1 month of enrollment and received a blood transfusion due to low hemoglobin, then the original test will dictate treatment group (high vs low risk).

¹⁶ Hemoglobin and platelet count will be assessed per SOC during treatment.

¹⁷ Blood sample for correlates will include assessments of C-reactive protein, KSHV viral load from plasma and PBMCs, and cytokine levels (IL-6, IL-10, IL-2, TNF α , INF γ). KSHC genotyping will occur on the first draw only. Blood draws will be two 10 mL tubes (2 heparin tubes separated into plasma and PBMCs) and 1 tube (5 mL) with citrate. Correlative blood samples collected during long term follow up will be stored and analyzed

¹⁸ In women under 60 years of age, required within 3 days of start of treatment.

¹⁹ At 12 and 24 month long term follow up visits.

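### Radiologic response is an endpoint at 12 weeks, but no chest X-ray or ultrasound is scheduled then, so imaging-dependent response categories cannot be updated at that visit

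*Combined protocol and SAP*

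**What the plan says.** Section 2.2 sets the objective (2.2.5): "To describe radiologic response rates at end of treatment and 12 weeks after start of treatment". Endpoint 3.2.5 keeps both times: "Radiologic response rate is the percentage of patients without relapse at end of treatment and 12 weeks from treatment initiation". It then gives CR, PR, SD and PD criteria as well. Section 10.5.2 refers to 7.1.7 for the response criteria and uses radiologic response as a covariate for EFS and OS in a Cox model, without naming a visit.

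On imaging, 7.1.7 requires a baseline chest film and abdominal ultrasound and one repeat: "Chest radiography and abdominal sonography will be repeated at completion of treatment". No condition is attached. In Table 7, the row "Chest X-ray and abdominal ultrasound" is marked under the initial visit or relapse column and under end of treatment. The 12-week and long-term cells are blank. Footnote 13 qualifies the end-of-treatment mark: "Omitted if no baseline abnormalities on chest x-ray and abdominal ultrasound".

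On scoring, 7.1.7 treats lesions seen only on film or ultrasound as non-target, and asks that each lesion be followed by the method used at baseline. For CR it adds: "Any non-target lesion evident by chest x-ray or ultrasound must also be documented to have resolved by repeat evaluation". PR requires that non-target lesions have not increased. PD includes a new lesion above 15 mm.

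Lymph node measurements and a focused examination are scheduled at 12 weeks in Table 7. Section 8.4, however, lists planned disease measurements at baseline, day 15, end of treatment and long-term follow-up, and leaves out 12 weeks.

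**The concern.** The 12-week time point is deliberate: the amendment summary records that assessment times were added to objective 2.2.5 and that a 12-week visit was specified to match the objectives and endpoints. The imaging schedule does not support that time point. Followed as written, the 12-week radiologic rate would combine a current nodal examination with an image taken weeks earlier, or with no post-baseline image at all.

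At stake is what the trial can claim from this rate. A patient whose chest or abdominal lesion clears between end of treatment and week 12 would not be credited with CR. A patient with a new, silent, non-palpable lesion could still be counted as responding. A reader of the report would take the word radiologic to mean that images had been taken at that time.

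**Working it through.** The plan states no figure on this point to reproduce. The check is a comparison of sections, a day count, and a range for the number of patients.

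**1. Endpoint against schedule**

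| Time | Radiologic response wanted (2.2.5, 3.2.5) | Nodes measured (Table 7) | Chest X-ray and ultrasound (Table 7) |
|---|---|---|---|
| Baseline | reference | yes | yes |
| End of treatment | yes | yes | yes, unless baseline was normal |
| 12 weeks | yes | yes | none |
| Relapse | not applicable | yes | yes |

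**2. Age of the last scheduled image at week 12**

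Inputs: last dose on day 22 (Table 1, no delays); end-of-treatment visit 7 to 14 days after the final dose (Table 7, footnote 3); 12 weeks from start = day 1 + 84 = day 85; visit window of 7 days either way (Table 7, footnote 2).

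- End of treatment: 22 + 7 = day 29 to 22 + 14 = day 36.
- Gap: 85 − 36 = 49 days to 85 − 29 = 56 days, or 7 to 8 weeks.
- With the window applied to the 12-week visit: 78 − 36 = 42 days to 92 − 29 = 63 days.

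**3. Which categories depend on an image at week 12**

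- *CR, normal baseline images:* there is no imaging lesion to resolve, so CR can be judged from the nodes.
- *CR, baseline lesion documented as cleared at end of treatment:* the repeat-evaluation condition carries no date and can be read as met. The 12-week nodes then decide.
- *CR, baseline lesion still present or not re-imaged at end of treatment:* the condition is unmet and nothing scheduled at week 12 can meet it. A new CR cannot be documented.
- *PR:* absence of increase in a non-target lesion seen only on imaging cannot be checked.
- *PD:* a new lesion visible only on imaging is missed, unless suspected relapse triggers the images in the relapse column.

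**4. How many patients**

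Let q be the share with an abnormal baseline image and r the share of those documented as cleared at end of treatment. The documents give neither, so both are assumptions. With 27 enrolled, patients in whom a new CR cannot be documented at week 12 number 27 × q × (1 − r). Patients with no scheduled image after baseline unless they relapse number 27 × (1 − q).

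| q | r = 0 | r = 50% | r = 80% | No image after baseline |
|---|---|---|---|---|
| 25% | 6.75 | 3.38 | 1.35 | 20.25 |
| 50% | 13.5 | 6.75 | 2.7 | 13.5 |
| 75% | 20.25 | 10.13 | 4.05 | 6.75 |

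The full possible range for the first quantity is 0 to 27. Section 8.4 restricts efficacy evaluation to treated patients with measurable disease who are re-evaluated, so 27 is a ceiling for the denominator.

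**The case against.** The strongest reply is that this is largely a matter of labelling. Endpoint 3.2.5 gives imaging a limited role, "Chest radiography and abdominal sonography will be used for staging", and 7.1.7 says how response is judged: "Response will be evaluated via complete survey of lymph nodes with measurements and physical assessment of other palpable masses with measurements". It makes imaging-only lesions non-target for a stated reason, poor reproducibility of radiographs in this setting. Nodes are examined at 12 weeks, so the intended measure is available. This stands, and it supports the wording fix: if the 12-week measure is a nodal examination, it should be named as one and should not carry a CR that depends on imaging.

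A reader might draw four stronger conclusions, none of which the documents support:

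- That CR cannot be established at 12 weeks in anyone. It can, when baseline imaging was normal or the lesion had cleared by end of treatment.
- That every patient with a baseline imaging lesion has 12-week CR fixed by the end-of-treatment film. Patients whose film cleared can still gain or lose CR on their 12-week nodes.
- That the 12-week rate cannot be computed. On the no-relapse wording of 3.2.5 it can, because relapse in 10.5.2 is a recurrent MCD attack requiring treatment and needs no film. That leaves 3.2.5 with two competing definitions, which is a separate reason to revise it.
- That later chest or abdominal progression goes wholly unseen. Examinations continue at 12 weeks and every 3 months, and images are scheduled at relapse. Only silent, non-palpable disease visible solely on imaging is missed, and that would not count as an EFS relapse.

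It is also fair to say that the omission of 12 weeks from 8.4 loses no data, since Table 7 collects the nodal measurements.

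**Conclusion.** The mismatch is real and narrow. The plan names a 12-week radiologic endpoint that its imaging schedule does not support. The effect is confined to the three gaps set out above: new CR in patients with unresolved or unrepeated imaging lesions, the PR condition for imaging-only lesions, and silent new disease. Footnote 13 also conflicts with the unconditional repeat in 7.1.7 and leaves patients with normal baseline images on nodal assessment alone at end of treatment too.

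The gap of 49 to 56 days assumes treatment without delay. The count of about 1 to 20 patients rests on assumed values of q from 25% to 75% and r from 0 to 80%; the true number could be zero. This is a descriptive secondary endpoint, so the point is minor. It changes what can be claimed at 12 weeks and leaves the primary safety endpoint and the sample size untouched.

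**What to change.** No added imaging is needed.

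- **2.2.5, 3.2.5, 10.5.2:** limit radiologic response to end of treatment. Define the 12-week measure as lymph-node response by physical examination, using the SPD of target nodes already collected at that visit, with no CR that depends on imaging.
- **3.2.5:** use the CR/PR/SD/PD criteria, by reference to 7.1.7, as the single definition, and drop the no-relapse definition.
- **7.1.7 and Table 7, footnote 13:** reconcile the two. State that patients with normal baseline images are classified at end of treatment on nodes alone.
- **8.4:** add 12 weeks to the list of disease measurements.
- **10.5.2:** name end-of-treatment response as the covariate in the Cox model.

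The cost is a wording amendment and the loss of a 12-week radiologic claim that the schedule does not support.

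### Section 7.1.7 records unequivocal progression of non-target lesions, but its PD rule never uses that code, names only nodes for growth, and conflicts with Section 3.2.5

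*Combined protocol and SAP*

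**What the plan says.** All of this is in the combined protocol and SAP.

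- **Targets (7.1.7).** Measurable disease is "at least one measurable pathologic lymph node or other mass that can be accurately measured by physical exam", so a target need not be a node.
- **Non-targets (7.1.7).** These are "All other lesions (or sites of disease), including lesions evident only by chest x-ray or ultrasound". They need not be measured, and "these lesions should be followed as 'present' or 'absent', or in rare cases 'unequivocal progression".
- **PD (7.1.7).** There are three limbs. The first is "Appearance of a new lesion(s) >15mm in diameter". The other two are "at least a 50% increase in SPD of more than one node, OR at least a 50% increase in diameter of a previously identified node", the node in the last limb being larger than 1 cm.
- **PR (7.1.7).** The SPD of the targets must fall by at least half, "without any increase in size of non-target lesions".
- **SD (7.1.7).** "Neither sufficient shrinkage to qualify for PR nor sufficient increase to qualify for PD".
- **PD (3.2.5).** The endpoint section gives a different rule: any new lesion, or growth of at least 50% in lesion size. It is not limited to nodes.
- **Use (10.5.2).** Radiologic response is judged by the criteria of 7.1.7, and its prognostic value for EFS and OS is tested in a Cox model.

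**The concern.** A code that assessors are told to record should lead to a response category. Non-target disease counts towards CR, because it must resolve, and towards PR, because any increase bars it. The code for its clear progression leads nowhere. The two growth limbs also leave out the non-nodal masses that the same section accepts as targets. Non-nodal disease is not remote in this population: the flare definition in Section 4.1.7 accepts hepatosplenomegaly in place of lymphadenopathy.

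At stake is whether some patients with evident progression are tabulated, and possibly modelled, with patients whose disease is stable. Two analysts following 7.1.7 and 3.2.5 could also classify the same patient differently.

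**Working it through.** The plan gives no figure on this point to reproduce. The check is to take typical patients through both PD rules as written.

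| Case | Section 7.1.7 | Section 3.2.5 |
|---|---|---|
| A. Non-nodal non-target lesion coded as unequivocal progression; targets unchanged | No PD limb met: SD | PD if growth is at least 50%, which cannot be shown unless someone measures |
| B. As A, but target SPD down 60% | PR barred by the non-target increase; PD not met; SD wording does not fit because shrinkage was sufficient. Unclassified, or SD by default | As A |
| C. Sole target is a palpable non-nodal mass, 20x20 to 30x30 mm | Growth limbs name nodes only: SD | PD |
| D. Known chest or abdominal node over 1 cm, measured, diameter up 60% | PD by the third limb | PD |
| E. Node as in D, not measured, coded as unequivocal progression | No limb can be shown to be met: SD | As A |
| F. New lesion over 15 mm | PD | PD |

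Arithmetic for case C:

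- Product of diameters: 20 x 20 = 400 mm² and 30 x 30 = 900 mm². 900/400 = 2.25, an increase of 125%.
- Diameter: 30/20 = 1.50, an increase of 50%.

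Section 3.2.5 does not say whether lesion size means diameter or area, but case C reaches 50% on either reading. The two sections therefore disagree on C. Cases A, B and E show that the code has no category of its own. Cases D and F show where 7.1.7 does work.

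What this reaches downstream:

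- **SD/PD split.** Affected directly.
- **Response rate in 3.2.5.** It is described as the percentage of patients without relapse. It changes only if PD is read as relapse, which the section does not say.
- **Cox model in 10.5.2.** Affected if response enters by category. If it enters as CR+PR against the rest, SD and PD sit together and nothing moves. The coding is not stated.
- **CR+PR rate.** Unchanged, because SD and PD are both non-response.
- **Primary endpoint (3.1).** Safety only; unchanged.
- **EFS.** Sections 3.2.3, 7.1.6 and 10.5.2 do not list radiologic PD as an event. Section 1.1 mentions progression but does not tie it to the 7.1.7 criteria.

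Size per patient: if all 27 planned patients were evaluable under Section 8.4, one reclassified patient would move the PD proportion by 1/27 = 3.7 percentage points. With fewer evaluable patients the step is larger; for example, 1/24 = 4.2 points.

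**The case against.** The strongest reply has four parts.

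- **The gap may be deliberate.** Section 7.1.7 is headed for gross lymphadenopathy and makes imaging-only lesions non-target because radiographic studies are hard to reproduce at this site. That is a fair reason not to apply a percentage threshold to them. It does not explain why a separate code for clear progression is collected and then not used, or why a palpable target mass, measured with calipers, is left out of the growth limbs.
- **Section 3.2.5 already covers growth of any lesion.** This is true for a measured mass. But 10.5.2 names 7.1.7 for the analysis, so the result is a conflict and not a remedy. For unmeasured lesions a 50% threshold cannot be verified.
- **Deep nodes are covered.** A reader might infer that all progressing chest or abdominal disease is scored as stable. The documents do not support that. The third PD limb applies to any previously identified node over 1 cm, target or not, and measuring non-targets is optional, not forbidden. What stands is that the same nodal progression is PD or SD according to whether someone measured it.
- **The impact is small.** Much of this stands. No objective is a PD rate. Apart from relapse visits, imaging is repeated only at end of treatment and is omitted if the baseline was normal (Section 8.1), so the code has few chances to arise from imaging.

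**Conclusion.** The point holds in a limited form. Under 7.1.7, the section named for the analysis, unequivocal progression of non-nodal or unmeasured non-target disease and growth of a non-nodal target mass do not meet PD. Such patients become SD by default, or are unclassified if their targets shrank by at least half. Section 3.2.5 gives a different answer for the target mass.

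The consequence is confined to the SD/PD split and, conditionally, to the 3.2.5 response rate and the Cox predictor. A reader might go further and infer that the EFS or safety results are distorted, or that a sizeable share of patients is affected. Neither is supported: the listed EFS events and the primary endpoint do not use radiologic PD, and the only guide to frequency is the plan's remark that such cases are rare. The number of patients is unknown, and so is the number evaluable for efficacy. The 3.7-point step per patient assumes that all 27 are evaluable.

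The conclusion rests on reading the 7.1.7 limbs literally. An assessor who informally treats the code as PD would avoid the problem, but by a rule that the plan does not contain.

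**What to change.** For the radiologic-response endpoint only, and before analysis:

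1. Reconcile the PD definitions in 7.1.7 and 3.2.5 into one rule, including the new-lesion limb, which has a size limit in 7.1.7 and none in 3.2.5.
2. Word the growth limbs so that they cover target lesions, whether node or other mass.
3. State the response category to which a recorded unequivocal progression of a non-target lesion leads. PD is the reading in line with the code's own wording. This also settles patients whose targets shrank by at least half.

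Section 5.7 lists disease progression among the reasons for ending treatment. Whether the endpoint definition is meant to apply there is for the sponsor to reconcile; this point proposes nothing on it.

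The cost is a few lines of protocol and SAP wording. No new data are needed, because the code and the target measurements are already collected. The downside is that the PD count may rise slightly.
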